**Table 4-2: Allowable ranges for imputation by variable**

Variable	Minimum value	Maximum value	Integer values only
PASI	0	72	No
IGA	0	4	Yes
PSD items (itch, pain, scaling)	0	10	No
Scalp IGA	0	4	Yes
mNAPSI	0	130	No
BSA	0	100	No
IGAxBSA	0	400	No
DLQI	0	30	Yes
PGADA	0	100	No
EQ-5D-3L VAS	0	100	Yes

Variable	Minimum value	Maximum value	Integer values only
WPAI dimension scores	0	100	No for variables: “Percent work time missed due to problem” and “Percent overall work impairment due to problem”. Yes for variables: “Percent impairment while working due to problem” and “Percent activity impairment due to problem”. These two variables can only take values that are multiples of 10.
PHQ-9	0	27	Yes

- The Week 16 results from the specified statistical analysis (e.g. stratified CMH, logistic regression) of each of the 100 imputed data sets will be combined for overall inference using Rubin’s rules, which account for the uncertainty associated with the imputed values (Rubin, 1987). This will be done using SAS PROC MIANALYZE.

Some key points to consider relative to the calculation of the odds ratios and corresponding confidence intervals are noted below:

If stratified CMH or logistic regression are used, the estimates of the odds ratios from the logistic regression model in step 3 follow a log-normal distribution, and a log transformation is needed to normalize these estimates since the procedures for combining results from multiple imputed datasets are based on the assumption that the statistics estimated from each imputed dataset are normally distributed. Therefore, the log of the odds ratio estimates from the logistic regression model are used when combining into a single inference (the use of PROC MIANALYZE in step 3). Appropriate transformations to the standard errors and p-values should also be made in order to get the correct confidence intervals, for the CMH test using the p-value for the general association the Wilson-Hilferty transformation should be used (Ratitch, 2013).

For other continuous efficacy variables, MI will be used to impute missing data when possible (see Section 4.2.1.3). If the imputation model cannot converge, LOCF will be used.

Further details about imputation for different analysis sets are below:

**Randomized Set:** When programming multiple imputations based on the RS, PROC MI will be used with a separate data set for each of the 2 randomized treatment groups (bimekizumab 320mg Q4W and secukinumab) including all scheduled assessment visits from Baseline to Week 48.

**Maintenance Set:** When programming multiple imputation based on the MS, PROC MI will be used with a separate data set for each of the 3 Maintenance Period treatment groups

(bimekizumab 320mg Q8W, bimekizumab 320mg Q4W, secukinumab) including all scheduled assessment visits from Baseline to Week 48.

Open-Label Set: When programming multiple imputations based on the OLS, PROC MI will be used with a separate data set for each of the 6 treatment sequences based on the combination of randomized treatment at Baseline, Maintenance Period treatment and OLE period treatment at Week 48 including all scheduled assessment visits from Baseline to Week 144. However, the summary values for the 4 treatment sequences based on the combination of randomized treatment at Baseline and OLE period treatment at Week 48 will be computed after the imputation steps

The Open-label Set 2: The analyses will be based on OC. Multiple imputation methods described above will not be applied.

#### **4.2.1.7 Missing data methods for assessing impact of COVID-19**

In order to assess the impact of the COVID-19 global pandemic on planned statistical analysis, additional sensitivity analyses will be performed for the secondary efficacy variable PASI100 response at Week 48. The sensitivity analyses in Section 8.2.3 will also still be performed, Assessments for the primary efficacy variable and for other secondary efficacy variables are at timepoints prior to Week 48 and will have been performed prior to the pandemic, therefore additional supplementary analyses of these variables are not necessary.

As described in Section 4.2.1, if a subject discontinues early from the study, all efficacy data that are collected later than 35 days after the last administration of study treatment will be treated as missing and subject to imputation as applicable. Thus if a subject discontinues from the study due to COVID-19 (general circumstances related to the COVID-19 pandemic or due to confirmed or suspected infection with the novel coronavirus) and the PASI assessment at Week 48 is later than 35 days after the last administration of study treatment, this will also be treated as missing.

If the PASI assessment at Week 48 is conducted by video call or telephone, this will be treated as missing since the validity and exchangeability of these assessment modalities has not been established. This will be determined according to collection of COVID-19 protocol deviations (including COVID-19 impact assessment) (see Section 3.4 for further details).

##### **4.2.1.7.1 Hybrid approach for assessing impact of COVID-19**

The main sensitivity analysis method to assess the impact of the COVID-19 pandemic on planned statistical analysis uses a hybrid approach and will be applied to the analysis of PASI100 response at Week 48 based on both the RS and the MS. If study subjects have missing PASI score at Week 48, then the imputation method is dependent on the reason for missingness as follows:

- If the data is missing due to COVID-19 then MI-MCMC/monotone regression will be implemented following the method described in Step 1 of Section 4.2.1.6 to impute the missing PASI score at Week 48.
- If the data is missing due to other reasons, then PASI100 response at Week 48 will be imputed as a non-response using NRI.

MI-MCMC/monotone regression will be implemented as described in Step 1 of Section 4.2.1.6 for all subjects in the respective analysis set. However when data is missing or the subject discontinued from the study due to other reasons than COVID-19, they will be considered as PASI100 non-responders at Week 48 for each imputation during Step 2 regardless of their MI-MCMC/monotone regression imputed value. Then Step 3 of Section 4.2.1.6 using stratified CMH can be applied for the PASI100 response at Week 48. If the PROC MIANALYZE leads to non-calculable results (ie, if there are a low amount of data missing or subjects dropped out due to COVID-19), this analysis will not be reported.

#### 4.2.1.7.2 Subgroup approach for assessing the impact of COVID-19

A supplementary sensitivity analysis method to assess the impact of the COVID-19 pandemic on PASI100 response at Week 48 will use a subgroup analysis approach and will be based on the MS. The COVID-19 pandemic subgroups are defined as:

- Week 48 visit date before COVID-19 pandemic start date (ie, prior to COVID-19 pandemic)
- Week 48 visit date on or after COVID-19 pandemic start date (ie, during COVID-19 pandemic)

Where:

- COVID-19 pandemic start date is 11 March 2020. (The date is chosen as the date the World Health Organization declared COVID-19 as a pandemic.)
- For subjects with a Week 48 visit, the actual date of the Week 48 PASI assessment will be used to determine subgroup inclusion.
- For subjects without a Week 48 visit, the scheduled Week 48 visit date will be used to determine subgroup inclusion, where:
  - Scheduled Week 48 visit date = date of first dose of study drug + 336 days.

Note:

- It is not anticipated that there will be any Week 48 visits post-pandemic for this study.
- Although the COVID-19 pandemic subgroups are determined based on an event occurring after randomization, the inclusion of a subject in the applicable subgroup is independent of their PASI assessment at Week 48 and is independent of the subject's Baseline characteristics.

This subgroup analysis for PASI100 at Week 48 will include descriptive statistics with missing data imputed using NRI.

#### 4.2.1.7.3 Approach to assess the impact of out of window assessments due to COVID-19

Another supplementary sensitivity analysis method to assess the impact of the COVID-19 pandemic on the planned statistical analyses will treat PASI assessments that are out of window at Week 48 due to COVID-19 as missing. A window of  $\pm 21$  days relative to the scheduled Week 48 visit will be evaluated. This will be applied to the analysis of PASI100 response at Week 48 based on both the RS and the MS.

The PASI assessment at Week 48 will therefore be determined as out of window due to COVID-19 if the following criteria are both met:

- There is a corresponding out of window COVID-19 protocol deviation (see Section 3.4 for further details)
- Date of first dose of study drug + 315 days > Week 48 PASI assessment date or Week 48 PASI assessment date > date of first dose of study drug + 357 days

A hybrid approach will then be applied as in Section 4.2.1.7.1 such that if the data is missing due to COVID-19 then MI-MCMC/monotone regression will be implemented and if data is missing due to other reasons, then PASI100 response at Week 48 will be imputed as a non-response using NRI. If the PROC MIANALYZE leads to non-calculable results, this analysis will not be reported.

#### 4.2.2 Handling missing data for safety variables

For analyses of AEs and concomitant medication usage, a complete date must be established in order to correctly identify the AE or medication as occurring during treatment or not. For purposes of imputing missing components of partially-reported or missing start and stop dates for AEs and for medication use, the algorithms listed below will be followed. Start and stop dates of AEs or concomitant medication will be displayed as reported in the subject data listings (i.e., no imputed values will be displayed in data listings).

Partial or missing AE and concomitant medication start dates will be imputed as follows:

##### Imputation of Partial or Missing Start Dates

- If only the month and year are specified and the month and year of first dose is not the same as the month and year of the start date, then use the 1st of the month
- If only the month and year are specified and the month and year of first dose is the same as the month and year of the start date, then use the date of first dose
- If only the year is specified, and the year of first dose is not the same as the year of the start date, then use the 1st of January of the year of the start date
- If only the year is specified, and the year of first dose is the same as the year of the start date, then use the date of first dose
- If the start date is completely unknown and the stop date is unknown or not prior to the date of first dose, then use the date of first dose
- If the start date is completely unknown and the stop date is prior to the date of first dose of IMP, then set the start date to the 1st of January of the year of the stop date.

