## 3.2 Definition of Baseline values

A Baseline value for a subject is defined as the latest measurement for that subject up to and including the day of administration of first study medication, unless otherwise stated. If a Baseline assessment is taken on the same day as first administration of study medication, it is eligible to be used as the Baseline value, even in the case that the time of the assessment is recorded as taking place after the time of first study medication administration. This is considered acceptable as this measurement is still the best representation of the Baseline value of the given assessment since it is highly unlikely that the study medication could have an impact on any measurement in such a short period of time. However, such cases should be rare as study center personnel are instructed to do all assessments at the Baseline visit prior to administering study medication. One exception to this rule is plasma concentration. If Baseline plasma concentration is measured at a time after the first administration of study medication, then it should not be eligible to be considered as a Baseline plasma concentration. Such cases should be discussed with the quantitative clinical pharmacologist.

If a Baseline measurement is missing or not collected, and a Screening value is available, the Screening value will be utilized as Baseline instead.

Baseline values for component scores should be computed using components from the same visit where the relevant measurements were recorded prior to dosing. For example, if the Screening visit has all of the components, but the Baseline visit is missing one or more components, the Baseline value for the component score should be calculated using the Screening visit values.

When the time of first dose is derived, it should be based on the first injection of study treatment, regardless of whether or not it is an active treatment.

Unless specified otherwise, the process laid out above will always be followed to determine Baseline. An additional Baseline value for the OLE Period will be defined for anti-bimekizumab antibodies for subjects initially randomized to secukinumab and for selected summaries of laboratory evaluations. This baseline for the OLE Period is the latest measurement on/prior to the day of first dose in the OLE Period for subjects switching from secukinumab to bimekizumab.

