## **3.6 Treatment assignment and treatment groups**

It is expected that subjects receive treatment as randomized and hence safety analyses will be based on the SS, as randomized. However, if after unblinding it is determined that subjects randomized to a treatment arm had never received such treatment, then for safety analysis, these subjects will be reallocated to the appropriate received treatment groups, unless otherwise specified.

If subjects randomized to secukinumab received bimekizumab at any time, then for safety analyses these subjects will be reallocated to the appropriate bimekizumab treatment group, unless otherwise specified. Subjects randomized to bimekizumab will only be reallocated to the secukinumab treatment group if they never received bimekizumab.

Efficacy analyses should be performed according to randomized treatment and not actual treatment received.

Randomized treatment groups are Bimekizumab 320mg Q4W and Secukinumab 300mg Q4W. Maintenance treatment groups are Bimekizumab 320mg Q4W, Bimekizumab 320mg Q8W, and Secukinumab 300mg Q4W.

Re-randomized (Open-Label extension) treatment groups are Bimekizumab 320mg Q4W and Bimekizumab 320mg Q8W. Unless otherwise specified, the OLE period will be summarized by treatment sequence comprising randomized treatment at Baseline and OLE period treatment at Week 48.

The following treatment sequences will be used to summarize efficacy data and specific safety data related to laboratory, ECG, PHQ-9, eC-SSRS, and vital signs assessments:

- Subjects receiving bimekizumab in the double-blind treatment period:
  - Initiating OLE on bimekizumab Q8W

- 
- Initiating OLE on bimekizumab Q4W
  - Subjects receiving secukinumab in the double-blind treatment period
    - Initiating OLE on bimekizumab Q8W
    - Initiating OLE on bimekizumab Q4W
  - All Subjects

Adverse event data (including for a subgroup of subjects who switched from Q4W to Q8W during OLE period) and study compliance data will be summarized in 2 treatment groups based on the dose most recently received prior to the date of the event or assessment

- Bimekizumab 320mg Q8W
- Bimekizumab 320mg Q4W
- Bimekizumab Total

In addition, the following key efficacy variables:

- PASI90 response
- PASI100 response
- IGA Clear or Almost Clear (with at least a 2-category improvement from Baseline)
- IGA Clear (with at least a 2-category improvement from Baseline)

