## 10.2 Adverse events

An AE is any untoward medical occurrence in a subject or clinical investigation subject administered a pharmaceutical product that does not necessarily have a causal relationship with this treatment. An AE can therefore be any unfavorable and unintended sign (including an abnormal laboratory finding), symptom, or disease temporally associated with the use of a medicinal (investigational) product, whether or not related to the medicinal (investigational) product.

Adverse events will be coded according to the MedDRA. AEs will be allocated to the respective randomized treatment arm. For subjects who switch treatment at Week 16, Week 48 or (on or after Week 64), any adverse events that occur after initiation of the new treatment are attributable to the new treatment. If an adverse event occurs on the date of a treatment switch, the event is attributed to the original treatment. The only exception to this is if the AE fulfills any of the criteria specified below:

- Events that fulfill the anaphylaxis criteria for acute events
- Events that fulfill the hypersensitivity criteria
- Events with an HLT of “Administration site reactions NEC”
- Events with an HLT of “Injection site reactions”

For results disclosure on public registries (eg, ClinicalTrials.gov), treatment-emergent adverse events and treatment-emergent serious adverse events will be published.

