### 10.2.2 AE summaries

AE summaries will be provided by actual treatment at the time of the adverse event. Separate AE summaries for OLE2 treatment period will be provided by treatment sequence as specified in Section 3.6 and will be based on OLS2.

For subjects who discontinue on or prior to the final scheduled visit of the Initial Treatment Period, any AEs that emerged more than after 112 days relative to the first dose but still within the 140 days SFU window will be classified as TEAE. However, these AEs will be excluded from AE summaries based on the Initial Period but included in the AE summaries for Initial and Maintenance Treatment Period. See the description of time at risk in Section 10.1.1 for further details.

The following selected outputs will be produced for the SS for the Initial Treatment Period, for the MS for the Maintenance Treatment Period, for the SS for the Initial and Maintenance Treatment Period, for the OLS for the Open-Label Extension Period:

- Incidence of TEAEs – Overview
- Incidence of TEAEs per 100 subject years by SOC, HLT, and PT

- Incidence of Serious TEAEs per 100 subject years by SOC, HLT, and PT
- Incidence of TEAEs Leading to Discontinuation per 100 subject-years by SOC, HLT and PT
- Incidence of TEAEs by decreasing frequency of PT

The following summaries will be provided for the SS for the Initial Treatment Period, for the SS for the Initial and Maintenance Treatment Period:

- Incidence of TEAEs Leading to Death by SOC, HLT, and PT
- Incidence of TEAEs by Maximum Relationship by SOC, HLT, and PT
- Incidence of Serious TEAEs by Relationship, SOC, HLT, and PT – Note: For European Union Drug Regulating Authorities Clinical Trials (EudraCT) reporting purposes
- Incidence of Related Serious TEAEs by SOC, HLT, and PT
- Incidence of TEAEs Leading to Death by Relationship by SOC, HLT, and PT – Note: For EudraCT reporting purposes
- Incidence of TEAEs by Maximum Severity, SOC, HLT, and PT
- Incidence of TEAEs Above Reporting Threshold of 5% by SOC and PT
- Incidence of Non-Serious TEAEs by SOC, HLT, and PT
- Incidence of Non-Serious TEAEs by Maximum Relationship SOC, HLT, and PT
- Incidence of Non-Serious TEAEs Above Reporting Threshold of 5% by SOC and PT
- Incidence of Non-Serious TEAEs Above Reporting Threshold of 5% by Relationship SOC and PT
- Incidence of Related TEAEs by SOC, HLT, and PT
- Incidence of Related TEAEs Above Reporting Threshold of 5% with Risk Differences by SOC and PT

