- Listing of COVID-19 Vaccine Interval TEAEs

The following summaries will be provided for the BKZ Set by treatment at the time of AE onset. These tables will include AEs from both the double-blind and Open-Label treatment period (excluding OLE2 treatment period). AEs that occurred while subjects received secukinumab will not be included.

- Incidence of TEAEs Overview
- Incidence of TEAEs per 100 Subject-Years
- Incidence of Serious TEAEs per 100 Subject-Years
- Incidence of TEAEs by decreasing frequency of PT

- Incidence of TEAEs per 100 subject years by SOC, HLT, and PT and by Time of Onset Relative to COVID-19 pandemic (prior to COVID-19 pandemic, during COVID-19 pandemic).

In addition, all summaries of TEAEs based on “100 subject years” will include EAIR (with 95% CI) and EAER.

The following summaries will be presented for subjects who switched from secukinumab to bimekizumab at Week 48. The analyses will assign AEs according to the AE onset date relative to last secukinumab dose and accounting for approximately 5 times half-life (Onset  $\leq$  140 days from last secukinumab dose or Onset  $>$  140 days from last secukinumab dose):

- Incidence of TEAEs Overview
- Incidence of TEAEs per 100 Subject-Years
- Incidence of Serious TEAEs per 100 Subject-Years

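### Month-only AE start dates are imputed against the Week 0 dose only, so those in the Week 48 switch month are charged to secukinumab even when the AE began on bimekizumab

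*SAP*

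**What the plan says.** **The imputation rule (SAP 4.2.2).** The purpose given is that "a complete date must be established in order to correctly identify the AE or medication as occurring during treatment or not". For start dates with month and year only, there are two branches. If the month is that of the first dose, the first-dose date is used. The other branch begins "If only the month and year are specified and the month and year of first dose is not the same as the month and year" when the AE began, and it sets the 1st of the month.

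**What first dose means.** Section 3.2: "When the time of first dose is derived, it should be based on the first injection of study treatment". Where the SAP means a later dose, as in the exposure rules of 10.1, it names the period. Section 4.2.2 never does.

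**How the date is then used.**
- Section 3.6 groups OLE adverse event data "based on the dose most recently received prior to the date of the event or assessment".
- Section 10.2 gives events after a switch to the new treatment, but: "If an adverse event occurs on the date of a treatment switch, the event is attributed to the original treatment". Anaphylaxis, hypersensitivity, administration-site and injection-site events are exempt from that switch-day rule.
- Section 10.2.2: "AE summaries will be provided by actual treatment at the time of the adverse event". For the BKZ Set tables: "AEs that occurred while subjects received secukinumab will not be included".

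**The concern.** The rule in 4.2.2 was written to decide whether an AE is on treatment at all. The same imputed date also decides which drug and which period the AE counts under, and no later first dose serves as an anchor for that. All secukinumab subjects who enter the OLE change drug at Week 48. If the day of onset is missing in that month, the rule resolves the doubt away from the investigational drug. At Week 0 the same doubt is resolved towards study drug. The OLE time at risk in 10.1.4.1 still starts at the first OLE dose, so an event can leave the bimekizumab numerator while its person-time stays in the denominator. At stake are the bimekizumab AE counts and rates just after the switch.

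**Working it through.** The plan states no figure on this point, so there is none to reproduce.

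**Inputs from the SAP**
- Week 48 timing (4.2.1.7.2): "Scheduled Week 48 visit date = date of first dose of study drug + 336 days". The ±21-day window in 4.2.1.7.3 gives 315 to 357 days.
- 350 subjects planned on secukinumab (2.3.2.2); this is a ceiling on switchers because the OLE is optional.
- OLE length 96 weeks = 672 days (2.3.2).

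**Assumptions, not in the SAP**
- Onset is uniform over the month, and the switch is equally likely on each of the 1,461 dates of a four-year cycle.
- 100 to 300 AEs per 100 patient-years, with 1% to 3% of start dates month-only.

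**1. Which branch applies.** Two dates in the same month and year are at most 30 days apart. Week 48 is at least 315 days after Week 0, so the months never match (0 of 1,461 dates at every gap from 315 to 357 days). The 1st-of-month branch always applies.

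**2. Illustration.** Week 0 on 10 Sep 2018 gives Week 48 on 12 Aug 2019. An AE that began on 20 Aug 2019, recorded only as Aug 2019, is dated 1 Aug 2019 and counted under secukinumab. With its full date it would count under bimekizumab.

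**3. Share affected.** For a switch on day s of a month with m days, s − 1 days lie before it, 1 on it and m − s after it. Averaged over the 1,461 dates these are 14.73, 1 and 14.73 days, or 48.4%, 3.3% and 48.4% of the month. Under 10.2 the 48.4% after the switch belong to bimekizumab. The rule gives bimekizumab none of them, apart from the exempt reactions when the switch is on the 1st (3.3% of dates).

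**4. Size.**
- 14.73 / 672 = 2.2% of a switcher's OLE days.
- 350 × 14.73 / 365.25 = 14.1 patient-years.
- Low end: 14.1 × 1 × 0.01 = 0.14 events. High end: 14.1 × 3 × 0.03 = 1.27 events.

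**5. Whether another rule repairs it.** The ambiguity clauses in 4.2.2 and 10.2.1 settle only treatment-emergent status; an AE dated under secukinumab already has that. The stop-date correction in 4.2.2 acts only if the stop precedes the imputed start, which cannot happen when the AE stopped in that month or later.

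**6. OLE2 entry.** Entry is not on the 1st for 96.7% of dates, so a month-only AE in the entry month is nearly always dated before OLE2.
- Group A: it is counted in the OLE. The drug is the same.
- Group B after a completed SFU: the last Q8W dose is at Week 136, then come a 20-week SFU and a 4-week screening, so the shortest nominal gap is 24 × 7 = 168 days. At that gap the 1st of the entry month is more than 140 days after the last OLE dose and before the first OLE2 dose for 88.7% of dates. Section 4.2.2 thus dates the AE into the off-drug gap, while 10.2.1 presumes an undatable AE to be treatment-emergent. The SAP does not say which period counts it.

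**7. What a new anchor would do.** Moving these AEs to the OLE first-dose date misassigns those that began before or on the switch day: 48.4% + 3.3% = 51.6% after rounding, against 48.4% now. If full stop dates are known, only pre-switch AEs still ongoing at the switch, plus on-day AEs, are misassigned. With geometric durations of mean D days, an AE that began k days earlier is still ongoing with probability (1 − 1/D)^k. Averaged over the same dates, the misassigned share is 18.5% for D = 7, 28.4% for D = 14 and 38.1% for D = 30, so about 19% to 38%.

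**The case against.** The strongest reply is that this hardly matters. About one event or fewer moves, both rates behind that figure are assumed, and 350 switchers is a maximum. That stands, and it sets the severity.

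A second reply is that secukinumab attribution is defensible. Section 10.2 already sends switch-day events to the original treatment, and 10.2.2 adds tables for these same switchers split at 140 days from the last secukinumab dose. That dose is at Week 44, so the switch month ends at most 28 + 30 = 58 days later, well inside the window. But the split is additional; it does not replace 10.2, under which a fully dated AE after the switch goes to bimekizumab. Only the missing day changes its drug.

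Third, the fix is not clearly more accurate. This stands in part: without usable stop dates it reverses the error rather than reducing it, and month-only stop dates, imputed to month-end, do not help. It also leaves the Week 16 and Q4W-to-Q8W switches under the present convention, though the drug does not change there.

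Fourth, a reader might infer that Group B events after the SFU drop out of both the OLE and the OLE2 summaries. The document does not support that. Section 10.2.1 presumes treatment emergence when partial dates leave it undecided; what is missing is a statement of the period.

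**Conclusion.** Wrong as written, and minor. Section 4.2.2 assigns every month-only AE in the Week 48 switch month to secukinumab, bar the exempt reactions when the switch is on the 1st. About 48% of them would have started on bimekizumab if onset is uniform, and every such error favours bimekizumab. The expected number is about 0.1 to 1.3 events under the assumed rates; the true number of partial dates is unknown. No efficacy or confirmatory result is affected, and listings keep the dates as reported.

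A reader might infer that OLE rates as a whole are biased downwards. That is not established. For Group A, OLE2 entry-month AEs are pulled into the OLE, which works the other way, and dating AEs to the 1st in other months shortens the exposure time used for the EAIR. The one-directional error is shown only at the Week 48 boundary. At OLE2 entry the question is the period label, not the drug.

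**What to change.** Add to 4.2.2, for AEs only:

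> If only month and year are known and they match those of the first OLE dose (both randomized arms) or the first OLE2 dose, and the reported or imputed stop date is missing or not before that dose, impute that dose date and assign the AE to the new treatment/period, as an exception to the switch-day rule in 10.2. An imputed day alone does not meet the anaphylaxis timing criterion.

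The exception to 10.2 is needed; without it the switch-day rule would send the AE back to the original treatment. Covering both randomized arms keeps the double-blind comparison symmetric. Stating the period also settles the Group B question.

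Leave the already reported Week 48 interim tables unchanged, and footnote any difference in re-run tables.

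The cost is a few lines of text and one branch in the date program. The downside is that some pre-switch AEs will be charged to bimekizumab, at the shares derived above. The gain is mainly that the remaining error runs in the conservative direction.
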